Statistical Analysis Plan

Title: Utilizing Protein During Weight Loss to Impact Physical Function and Bone

NCT03819478

Date: 04/24/2023

Statistical Analysis Plan

We expect to enroll 225 participants in the study. Retention is expected to be $\geq 90\%$ at 6 months (≥ 67 completers/group) and $\geq 80\%$ at 18 months (≥ 60 completers/group) based on compliance rates of prior weight loss and exercise trials conducted at the Wake Forest School of Medicine (WFSM). All statistical analyses will be performed in SAS or R. Before performing hypothesis testing, data distributions will be examined to determine if transformations are necessary and if nonparametric approaches should be used. Analyses will conform to intent-to-treat principles, indicating that participants will be included in analyses according to the groups to which they were randomized. The models will include a random effect for wave to account for the potential correlation of participants within waves.

Volumetric BMD and Cortical Thickness Outcome Measures at Primary Endpoint of 18 months

The study is $\geq 80\%$ powered ($N=180$, 2-sided $\alpha=0.025$) to detect differences in change between groups of 0.016 g/cm^3 ($SD=0.028$ g/cm^3) and 0.007 g/cm^3 ($SD=0.013$ g/cm^3) volumetric bone mineral density (vBMD) and 0.063 mm ($SD=0.111$ mm) and 0.018 mm ($SD=0.032$ mm) cortical thickness at 18 months at the spine and hip, respectively (SDs of change from preliminary data).¹ Mean group differences and effect sizes at 80% power are reported in **Table 1** for the expected 18-month sample size ($N=60/\text{group}$), as well as smaller sample sizes in the event of shortfalls in enrollment or retention ($N=30$, 40 , and $50/\text{group}$). Effect sizes ≥ 0.80 have been observed in prior trials that have detected statistically significant differences in lumbar spine BMD (0.92 - 1.60 effect sizes)²⁻⁴ and hip BMD (0.80 effect size)^{2,3} between higher versus lower protein groups, suggesting that our study is adequately powered to detect differences even with $N=30/\text{group}$.

We will use analysis of covariance (ANCOVA) to compare group effects on vertebral and femoral vBMD and cortical thickness at the primary endpoint of 18 months, with adjustment for baseline values. Age, sex, race, and baseline value of the outcome of interest will be adjusted for as covariates in these analyses.

Bone marrow adipose tissue outcomes have never been measured with moderate weight loss in a randomized controlled trial of older adults; thus, we do not have prior studies from which we can estimate power and effect sizes for the bone marrow adipose tissue secondary outcomes. However, as noted in **Tables 1 and 2**, we will have 80% power to detect effect sizes of 0.57 when comparing 3 groups of 60 individuals, and of 0.45 when comparing two groups of 60 and 120 individuals.

Analyses of will use ANCOVA to compare the group effects on bone marrow adipose tissue fraction and marrow-corrected vBMD at 18 months, with adjustment for baseline values. To examine the trajectory of change over time, we will compare bone marrow adipose tissue fraction and marrow-corrected vBMD by group and time using mixed-model ANCOVA with a random subject effect and a time-by-group interaction will be used to evaluate changes at 6 months and 18 months, using linear contrasts to compare the three groups at each time point. We will adjust for age, sex, race, and baseline values of the outcome of interest as covariates in these analyses.

Bone Strength Outcome Measures

Bone strength and fracture risk outcomes are predicted from finite element modeling. The study is $\geq 80\%$ powered ($N=180$, 2-sided $\alpha=0.025$) to detect differences in change between groups of 0.037 kN ($SD=0.065$ kN) for femoral bone strength (SDs of change from preliminary data). Mean group differences and effect sizes at 80% power are reported in **Table 3** for the expected 18-month sample size ($N=60/group$), as well as smaller sample sizes in the event of shortfalls in enrollment or retention ($N=30$, 40, and 50/group). Fracture risk is a dichotomous outcome, where fracture is predicted in the finite element modeling simulations when elements exceed an effective plastic strain threshold; thus, estimated power and effect sizes are not provided for the fracture risk secondary outcomes.

Analyses of will be analogous to the other outcome analyses described earlier. ANCOVA will be used to compare the group effects on femoral bone strength and fracture risk at 18 months, with adjustment for baseline values. To examine the trajectory of change over time, we will compare femoral bone strength and fracture risk by group and time using mixed-model ANCOVA with a random subject effect and a time-by-group interaction will be used to evaluate changes at 6 months and 18 months, using linear contrasts to compare the three groups at each time point. We will adjust for age, sex, race, and baseline values of the outcome of interest as covariates in these analyses.

Table 3. Power to detect significant differences in mean change between groups at 18 months with ANCOVA (2-sided $\alpha=0.025$ after Bonferroni correction for each outcome), assuming similar SD between groups.

Outcome Measures	SD of Change	Power	Mean Group Difference (Effect Size; Diff/SD)			
			n=30/group	n=40/group	n=50/group	n=60/group
Femoral bone strength (kN)	0.065		0.053 (0.81)	0.046 (0.70)	0.041 (0.63)	0.037 (0.57)

Exploratory Analyses

We will use the mixed model framework to evaluate associations between weight loss and changes in bone phenotypes of interest, adjusting for age, sex, intervention group, and baseline values.

References

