Data analysis: Initial analyses will follow the “intent-to-treat” principle in which data from all randomized participants are analyzed according to their randomized groups. Analysis of covariance (ANCOVA) will be used for both primary and secondary aims to compare the group effect on change in expSPPB and muscle strength (primary aim) and weight loss maintenance, total and appendicular lean mass and fat-to-lean mass ratio, and thigh muscle volume and inter-muscular adipose tissue (IMAT) (secondary aim) at 18 months. Group contrasts will be constructed and tested within each model. ANCOVA will also be used to compare physical function, weight and body composition at 6 months. To explore whether differences in lean mass mediate the effect of a higher protein diet during and subsequent to weight loss on physical function, change in lean mass will be added to the ANCOVA models to assess whether the intervention effect is reduced or eliminated as an ad hoc mediation analysis. To compare the exploratory outcomes (bone mineral density and cardiometabolic risk factors) at 6 and 18 months, ANCOVA with repeated measurements will be used, and correlations between 6 and 18 months taken into account using a compound symmetry covariance structure. All models will be adjusted for the baseline measure, age, gender, and race.

Factors that may influence the measured responses to the interventions (e.g., initial body weight or composition, changes in weight, physical activity, etc.) will be evaluated and possibly included in secondary analyses. We will also consider conducting analyses adjusted for intervention process measures (such as dietary intake, average attendance at diet and exercise sessions, and protein intake/urinary nitrogen) to examine the extent to which these contribute to the outcomes.

Planned sensitivity analyses to assess the impact of COVID19: Because of the potential impact of COVID19 on intervention delivery and follow-up assessments, we plan to conduct several sensitivity analyses:

- 1) Exclude Wave 13 and 14 participants (n=26) whose intervention was interrupted by the COVID19 research pause on March 13, 2020, and who completed the last ~2 and ~4 months, respectively, of the exercise portion of the 6-month intervention on their own while attending the diet portion of the intervention remotely (via phone).

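### Predicted fracture is a yes/no outcome, but the SAP analyses it with constant-variance ANCOVA and names no binary model, robust variance or effect measure.

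*SAP*

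**What the plan says.** In the SAP, Bone Strength Outcome Measures, the outcome is defined as binary: "Fracture risk is a dichotomous outcome, where fracture is predicted in the finite element modeling simulations when elements exceed an effective plastic strain threshold". The SAP gives this as its reason for omitting power: "estimated power and effect sizes are not provided for the fracture risk secondary outcomes".

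The next paragraph assigns it the same model as femoral strength in kN: "ANCOVA will be used to compare the group effects on femoral bone strength and fracture risk at 18 months, with adjustment for baseline values". Over time, "we will compare femoral bone strength and fracture risk by group and time using mixed-model ANCOVA with a random subject effect", with a time-by-group interaction and "using linear contrasts to compare the three groups at each time point". Covariates are age, sex, race and the baseline value. The SAP's opening paragraph adds a random wave effect to all models.

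The nearest general provision is in that opening paragraph: "data distributions will be examined to determine if transformations are necessary and if nonparametric approaches should be used". Neither document names a logistic or other binary model, a robust variance, or an effect measure for this outcome.

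**The concern.** The SAP treats the binary nature of the outcome as a reason to omit power figures, but not as a reason to change the model. ANCOVA on a 0/1 variable is a linear probability model, so its contrasts estimate risk differences. The weak point is the standard error. Ordinary ANCOVA pools one residual variance over the three arms, whereas each arm's true variance is p(1−p). A pairwise contrast is therefore mis-scaled whenever the average p(1−p) of its two arms differs from the three-arm average. In a mixed model with one residual variance across visits, the same happens when prevalence changes between 6 and 18 months, even if all arms are identical.

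Some p-values and intervals would be too optimistic and others too conservative, and a reader could not tell which. The comparison of 6-mo with 18-mo HiProt when RecProt differs is one such case. The provision on transformations and nonparametric approaches does not help: no transformation gives a 0/1 variable constant variance, and the choice would come after the data are seen.

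**Working it through.** **The section's own figure.** Table 3 concerns femoral strength only. A two-sample noncentral-t calculation (SD 0.065 kN, 60 per group, two-sided 2.5%, 80% power) gives an effect size of 0.569, and 0.569 × 0.065 = 0.037 kN, as stated. Nothing comparable exists for fracture risk.

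**Inputs.**
- n = 50 per arm: Protocol, Sample size, 187 enrolled less 20% drop-out; 187 × 0.8 / 3 = 49.9.
- Nominal 2.5%, two-sided: borrowed from SAP Table 3 ("after Bonferroni correction for each outcome), assuming similar SD between groups"). No level is stated for fracture risk itself.
- Fracture risks: assumed throughout.

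**Standard-error ratio, 18-month contrast of arms i and j.** The model's variance tends to (2/n) × the mean of p(1−p) over three arms. The true variance is (2/n) × the mean of p(1−p) over arms i and j. Hence

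ratio = √(three-arm mean / pair mean), and rejection ≈ 2[1 − Φ(2.241 × ratio)].

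- 20/20/10%: p(1−p) = 0.16, 0.16, 0.09; three-arm mean 0.1367; ratio √(0.1367/0.16) = 0.92; about 3.8%.
- 10/10/20%: 0.09, 0.09, 0.16; three-arm mean 0.1133; ratio √(0.1133/0.09) = 1.12; about 1.2%.

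**Exact rates.** These enumerate all 51³ outcomes with a pooled-variance t contrast on 147 df. Rejection means that the interval excludes the true difference.

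| Assumed risks (%) | Contrast | Rejection (nominal 2.5%) |
|---|---|---|
| 10, 20 or 30 in all arms | any | 2.4, 2.5, 2.5% |
| 20/20/15 | equal arms | 3.1% |
| 30/30/25 | equal arms | 2.8% |
| 10/10/15 | equal arms | 1.6% |
| 20/20/10 | equal arms | 3.9% |
| 10/10/20 | equal arms | 1.1% |
| 10/15/20 | outer; adjacent | 2.4%; 1.5% and 3.6% |
| 30/25/20 | outer; adjacent | 2.5%; 3.1% and 2.0% |
| 20/20/2 (extreme) | equal arms | 5.9% |
| 5/5/30 (extreme) | equal arms | 0.1% |

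With 60 per arm the pattern is the same (20/20/15 3.1%, 20/20/10 3.9%, 10/10/20 1.1%).

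**With the SAP's covariates and random wave.** Simulation used 10,000 replicates per case and 17 waves. It assumed a baseline-status odds ratio of 6 and, on the logit scale, a wave SD of 0.3 and a subject SD of 1.2. Monte Carlo error is about 0.16 points. The two-visit model has one residual variance.

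| Case | 18-month ANCOVA | Two-visit mixed model |
|---|---|---|
| Equal 20% | 2.4% | 2.3% |
| 20/20/15 | 3.1% | 3.1% |
| 20/20/10 | 3.6% | 3.5% |
| 10/10/20 | 1.3% | 1.4% |

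**Risk changing between visits, arms identical.** The fitted variance is the average over the two visits. For 10% moving to 15%, it is (0.09 + 0.1275)/2 = 0.10875 against a true 18-month value of 0.1275. The ratio is √0.853 = 0.92, which implies about 3.8%.

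| Risk, 6 to 18 months | Mixed model (simulated) | 18-month data alone |
|---|---|---|
| 10 to 15% | 4.0% | 2.8% |
| 15 to 20% | 3.6% | 2.8% |
| 10 to 20% | 4.5% | 2.4% |
| 20 to 10% | 0.9% | 2.2% |

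**The replacement.** In the cases equal 20%, 20/20/15, 20/20/10 and 10/10/20 (about 8,000 replicates, no wave effect), standardised logistic regression with robust variance gives 2.1, 2.1, 2.0 and 1.5%. Ordinary ANCOVA in that simulation gives 2.3, 2.8, 3.7 and 0.9%. Binomial GEE with robust variance (about 5,000 replicates, wave in the data but not in the model) gives 1.4–2.4%, including 2.4, 2.3 and 1.9% for risk moving 10 to 15, 10 to 20 and 20 to 10%. Replicates with no event in an arm (for GEE, at any visit), at most about 2%, were left out.

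**The case against.** The distortion is hypothetical and often small. No fracture proportion is documented, equal risks of 10–30% give almost nominal error, and five-point gaps give only 1.6–3.1%. Low risk is plausible, because Protocol Table 1 excludes osteoporosis. With equal arms at 5% or 2%, ANCOVA is conservative (1.8% and 0.6%), partly because sparse data are discrete, and a change of variance estimator does not cure that. The 2.5% level is inferred. The mixed-model figures assume one residual variance across visits. The SAP states no residual structure, and the compound-symmetry statement in the Protocol's Data analysis section ("correlations between 6 and 18 months taken into account using a compound symmetry covariance structure") concerns other outcomes. A lighter remedy exists: adding HC3 robust variance to the SAP's own linear model gives 1.8–2.3% in the adjusted 18-month simulations. The fuller remedy is itself slightly conservative, and it was not tested with wave in the model or with the sparse-event fallback.

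These points stand as limits on size, and the lighter remedy would be adequate at 18 months. They do not remove the mismatch. The SAP specifies no robust variance, the error changes direction with risks nobody has stated, and a one-variance mixed model errs even with no diet effect if prevalence moves.

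**Conclusion.** The concern holds. The SAP applies a constant-variance linear model to an outcome that it defines as binary, and the effect measure is left unnamed. At a nominal 2.5%, gaps of five to ten points between arms move the error rate of some contrasts to between about 1.1% and 3.9%. A five- to ten-point change in risk between visits moves the mixed-model rate to between 0.9% and 4.5%. These sizes rest on assumed risks, about 50 completers per arm, the level borrowed from Table 3 and, for the mixed model, one residual variance. The standard error is close to right when all arms share a risk of about 10–30%, and for the outer contrast when risks are evenly spaced. The outcome is secondary and unpowered; vBMD, cortical thickness and continuous femoral strength are untouched. It should be fixed, but it does not threaten the main bone results.

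**What to change.** Keep ANCOVA for femoral strength only. For fracture risk, the SAP should:

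- name the risk difference as the effect measure and state the test level;
- at 18 months, use logistic regression adjusted for baseline fracture status, age, sex and race, standardised to a marginal risk difference with heteroscedasticity-robust variance (the SAP's linear model with robust variance is an acceptable lighter choice here);
- for 6 and 18 months, use a binomial GEE with group-by-time and robust variance, standardised to the same risk difference at each visit;
- say how wave enters these models;
- fix one sparse-event fallback and its trigger in advance, for example Firth-penalised logistic regression with intercept correction and baseline status as the only covariate, used if any arm has fewer than 5 predicted fractures.

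The cost is a few sentences and a different procedure in the same SAS or R software, with no new data. The price is slightly conservative tests at low risks and slightly more analysis work.
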